18.1. Participant Recruitment

Patients will be initially contacted by the Practice and their identity only disclosed to the researchers once they return the consent form and primary outcome questionnaire to the study team. We assume that ability to complete the questionnaire and respond to the invitation letter implies capacity, whether provided with or without the help of a carer/guardian.

18.2. Inclusion & Exclusion Criteria

We designed inclusion criteria with the aim of broadest reach to maximise inclusivity. For example, we included survivors regardless of the severity of their stroke. However, due to the nature of research and the service offered, we recognise that certain groups of patients will most likely be excluded. For example, patients in living in nursing care homes may not be able to benefit from the components offered (e.g. referrals to other services). We therefore chose to exclude these groups.

18.3. Utilisation of the Model

The structured review will confer minimal additional burden to participants as it will be performed as part of the annual review. Patients may bring an informal caregiver to the review.

The MLAS service and direct point of contact is offered as an additional, opt-in service component which patients may use at their discretion.

18.4. Questionnaires

All the questionnaires are finding out complementary information of importance to evaluating the impact of the model. A full set of questionnaires should take no longer than 10 - 30 minutes to fill in during baseline and 45 minutes at follow-up. Patients are clearly informed in the Participant Information Sheet (PIS) about the flexibility of filling in the questionnaires in multiple sittings.

Information disclosed in the questionnaires will be kept confidential, anonymised and stored separately from patient identifiable data (PID; see data storage and confidentiality). The questionnaires (SIS, EQ-5D-5L, ICECAP-A, SSSQ, HLQ) do not include sensitive screening information and have been either used in large stroke trials or observational studies which included stroke patients.

18.5. Consent

The patient information sheet explains that their General Practice is taking part in a research study evaluating different models of care for stroke. It is entirely up to the patient to decide whether or not they wish to take part in the study. We are seeking consent to send them some questionnaires, possibly contact them by phone, and review their medical records. Patients will be sent a consent form by post (with an opportunity to contact the research team if they have any questions about the study).

19. Patient and Public Involvement (PPI)

Patient representatives were involved in the initial conception of the programme prior to funding submission. This included a patient representative attending the initial writing group plenary and two public workshops with stroke survivors and their carers.

Stroke patients and their carers were involved throughout the subsequent qualitative development work through interviews (n=36) and focus groups (n=19). Likewise, healthcare professionals including primary care representatives were engaged in 9 focus groups. This qualitative work was used to understand the current experience of primary care for stroke survivors and their carers and inform model components such as the structured review, checklist of stroke needs, and direct point of contact. In addition, we have consulted several local stroke support groups (Bedford, Bradford, Cambridge and London) during the development of the model. A multidisciplinary team of clinicians involved in stroke care, including a patient representative, has been regularly consulted on the model throughout the developmental stages.

Continued PPI will be achieved through the Trial Steering Committee which includes a patient representative. Some PPI members have also expressed an interest in becoming facilitators for the "My Life After Stroke" course which we will seek to achieve.

20. Approvals

Favourable ethical opinion for the research will be sought via Health Research Authority (HRA) prior to the recruitment of participants commencing at any NHS site.

Any subsequent amendments to study documentation, along with safety, annual progress and final study reports will be submitted to R&D and REC for information and/or approval, as required.

21. Dissemination

Dissemination will be via peer-reviewed journals and presentation at relevant conferences and local stroke groups. Participants will also receive a summary copy of the results, if they so wish.

22. References

I need advice on changes to lifestyle or medications for preventing another stroke.									
2. Activities of Daily Living (ADL)									
 I have difficulty dressing, washing and/or bathing. I have difficulty preparing hot drinks and/or meals. I have difficulty getting outside. 									
3. Mobility									
 I am finding it difficult to walk. I am finding it difficult to move safely around the house. 									
4. Pain									
I experience physical/muscular pain.I have headaches.									
5. Stiffness									
I find that my arms, hands, and/or legs are stiff.									
6. Incontinence									
I am having a problem controlling my bladder or bowels.									

	↓								
7. Communication									
 I am finding it difficult to understand / communicate with others. 									
 I have problems with speech, word finding or talking to others. 									
 I lack confidence when talking to others either in person or over the phone. 									
8. Mood									
 I feel anxious or depressed. 									
 I feel that my personality since stroke has changed. 									
9. Cognition									
I find it difficult to think, concentrate, or remember things.									
10. Relationships with Family									
My personal relationships with my family have become difficult or stressed.									
11. Fatigue									
 I feel tired most of the time or I get easily tired. I find it difficult to concentrate and do things. 									
12. Intimate relationships									
Since my stroke I have problems with sex.									
13. Work									
 others. I lack confidence when talking to others either in person or over the phone. 8. Mood I feel anxious or depressed. I feel that my personality since stroke has changed. 9. Cognition I find it difficult to think, concentrate, or remember things. 10. Relationships with Family My personal relationships with my family have become difficult or stressed. 11. Fatigue I feel tired most of the time or I get easily tired. I find it difficult to concentrate and do things. 12. Intimate relationships Since my stroke I have problems with sex. 13. Work I am having problems at work or I would like support and advice on returning to work. 									
14. Social activities									
I find it difficult to take part in hobbies or leisure activities.									

15. Have you noticed anything else that you are concerned about?

Primary Care Model

Anticipated Patient Recruitment Flowchart

Appendix C

	RCT Gantt Chart - Developing Primary Care Services for Stroke Survivors																																	
Workstream 3: Evaluation of the interventions		Starting 01/04/2017									Year 2 (from 01/04/2018)												Year 3 (from 01/04/2019)											
Summary of Activities	Apr 17		Jul 17			Oct 17			Jan 18			Apr 18			Jul 18			Oct 18			Jan 19		Apr 1	9		Jul 19			Oct 19			Jan 20		
Set up RCTs (REC, R&D approvals)																																		
Recruit Practices and train staff to deliver interventions																																		
Recruitment of participants																																		
Delivery of interventions																																		
6 Months follow-up of participants (patients)																																		
12 months follow-up of participants (patients)																																		
Data analysis, write-up & dissemination of findings

TSC	Trial Steering Committee

# 4 Introduction

# 4.1 Preface

No formal Primary Care based model of care exists to support stroke survivors living in the community. A large variation in the range, quality and access to health services offered to stroke survivors between and within local primary care trusts suggests that many of the stroke survivors' needs are not being met systematically. Therefore, to address the longer-term needs we have developed a multi-factorial Primary Care model that seeks to enable greater engagement with stroke care and community services, to link effectively to specialist services, and to improve the lives of stroke survivors.

# 4.2 Purpose of the analyses

These analyses will assess the efficacy and safety of a novel model of primary care for stroke survivors living in the community compared to standard care. A health economic analysis plan (HEAP) will be documented separately.

# 5 Study Objectives and Endpoints

# 5.1 Study Objectives

The main aim of the IPCAS trial is to evaluate the clinical and cost effectiveness of a novel model of primary care for stroke survivors living in the community.

The primary objective is:

• To assess the clinical effectiveness of the new model of primary care for stroke survivors compared with standard care. The two co-primary endpoints for the trial will be two subscales (emotion and handicap) of the Stroke Impact Scale (SIS v3.0) at 12 months.

The secondary objective is

• To assess the long-term cost effectiveness of the new model of primary care for stroke survivors compared with standard care.

#### 5.2 Endpoints

The primary endpoint for the trial will be two sub-scales (emotion and handicap) of the Stroke Impact Scale (SIS v3.0) as co-primary outcomes at 12 months.

Secondary endpoints include data collected via a series of questionnaires at baseline, 6 months and 12 months, comprising:

- SIS short form
- EuroQol EQ-5D-5L
- ICEpop CAPability measure for Adults (ICECAP-A)
- Southampton Stroke Self-management questionnaire (SSSMQ)\*
- Health Literacy Questionnaire (HLQ)\*
- \* Only collected at 12 months follow-up.

Secondary endpoints to examine cost-effectiveness will be collected, and details of these and any planned health economic analyses will be detailed by the health economist (they are beyond the scope of this SAP).

# 6 Study Methods

#### 6.1 General Study Design and Plan

The IPCAS trial is an open-label, two-level cluster randomised trial of patients clustered within general practices, with randomisation occurring at the level of the general practice.

General practices are randomised in a ratio of 1:1 to the control or experimental group. General practices in the control arm offer standard care to their patients. General practices in the experimental arm offer a novel model of care to their patients. Once all invitation letters and reminders are sent out to patients in a general practice, the general practice can be randomised.

Randomisations are performed using a stratified, random permuted block design. The stratification factor is general practice list size, split into two levels based on the approximate median general practice list size for the geographic areas likely to be included in the trial. The two strata levels are:

- i) Strata 1: General practice list size less than 10,500 patients;
- ii) Strata 2: General practice list size equal to or greater than 10,500 patients.

Random permuted blocks are used in order to maintain close balance in the allocation of the two treatment groups within each strata, and to minimise opportunities for selection bias. The exact block sizes used to produce the randomisation lists is documented separately by the statistician in order to help maintain blinding.

The sequence of key study points is summarised in the following flow chart.

# 6.2 Inclusion-Exclusion Criteria and General Study Population

As this is a two-level cluster trial, there are two levels at which the inclusion and exclusion criteria apply: the general practice level and the individual patient level.

General practices from the East of England and the East Midlands were eligible to take part in the IPCAS trial. Practices representing a range of urban/rural and different socio-economic status were identified, with a particular focus on practices with a stroke register comprising a minimum of 100 patients (to ensure that we maintain a target cluster size of 16-24 patients where possible).

For individual patients, the following inclusion/exclusion criteria apply:

#### Inclusion criteria

- On practice register with a history of stroke
- Able to provide written informed consent (with or without the help of a carer)
- Age 18 years or older

#### Exclusion criteria

- Patients on the palliative care register
- Living in a nursing home

The inclusion criteria were designed with the aim of achieving the broadest reach to maximise inclusivity. For example, we included survivors regardless of the severity of their stroke. However, due to the nature of research and the service offered, it was recognised that certain groups of patients would most likely be excluded. For example, patients living in nursing care homes may not be able to benefit from the components offered (e.g. referrals to other services). These groups were therefore excluded from taking part in the IPCAS trial.

#### 6.3 Blinding

The IPCAS trial is open-label due to the nature of the intervention under investigation. As this trial is open-label, there is the potential for bias related to knowledge of the treatment arm assigned to each cluster (general practice) by patients, carers, clinicians and the study team, particularly so because some of the endpoints, including the two co-primary endpoints, are subjective. In addition, blinded treatment outcome assessment for individual patients is not feasible due to the cluster-randomised nature of the trial, and because the co-primary endpoint scores are chosen by the patients themselves or their carer (so an independent assessor cannot be used). This is a limitation of the trial and will need due consideration when interpreting the results upon conclusion of the trial.

Blinding with respect to randomisation is discussed in section 6.4.

#### 6.4 Randomisation

The IPCAS trial is an open-label, two-level cluster randomised trial of patients clustered within general practices, with randomisation occurring at the level of the general practice. General practices will be randomised in a ratio of 1:1 to the control or experimental group.

Randomisation will be performed using a stratified, random permuted block design. The stratification factor will be general practice list size, split into two levels based on the approximate median general practice list size for the geographic areas likely to be included in the trial. The two strata levels are:

- iii) Strata 1: General practice list size less than 10,500 patients;
- iv) Strata 2: General practice list size equal to or greater than 10,500 patients.

Random permuted blocks will be used in order to maintain close balance in the allocation of the two treatment groups within each strata, and to minimise opportunities for selection bias. The exact block sizes used to produce the randomisation lists will be documented separately by the statistician and access to this document will be restricted.

Randomisation will be set up and administered by the MRC Biostatistics Unit. An individual randomisation list will be produced programmatically for each strata level using random permuted blocks. A random number seed will be used in the production of the randomisation lists and, for reproducibility purposes, this will be recorded at the time the randomisation lists are generated.

The statistician will maintain the randomisation lists and access to the randomisation lists will be restricted to the statistician plus other appropriately trained and delegated members of staff. A back-up randomiser will be nominated to cover periods when the trial statistician is on leave. Members of the operational trial team will not have access to the randomisation lists, but only the outcome of randomisation as each general practice is randomised.

To randomise a cluster, a designated person from the trial team will contact the statistician. They will provide the name of the cluster and the cluster size. The statistician will then refer to the relevant randomisation list for the stratum concerned, choosing the next unallocated treatment arm on the list. This treatment arm will then be assigned to the cluster. The statistician will communicate the allocated treatment arm to the designated person from the trial team in writing, and a record of this will be maintained by the statistician.

As the trial is open-label, procedures for emergency unblinding are not needed.

An audit trail of all randomisation requested and performed will be maintained by the statistician or other appropriately trained and delegated members of staff.

Access to restricted randomisation documents, including the block sizes, random number seeds and randomisation lists, will be made available at the end of the study.

#### 6.5 Study Variables

The frequency and timing of the main variable assessments is outlined in the Table 1. The primary outcome data will be collected via postal questionnaire at the time of invite to the study prior to Practice randomisation. Secondary outcome data (SIS Short Form, EuroQol EQ-5D-5L, and ICEpop CAPability measure for Adults (ICECAP-A)) will also be collected by postal questionnaire after randomisation. Non-responders to the secondary outcome questionnaire will be followed-up by telephone.

Follow-up via postal questionnaire will take place at six months after entry into the trial. These will include all of the baseline instruments. Non-responders will be followed up by telephone.

Follow-up at twelve months will comprise a combination of postal and telephone administered questionnaires including all of the baseline instruments plus the Southampton Stroke Self-

management questionnaire (SSSMQ) and the Health Literacy Questionnaire (HLQ). Non-responders to the postal questionnaires will be followed up by telephone.

Study assessment	Throughout	Baseline	6 months	12 months
Demographics (age, gender, etc)		х		
SIS short-form questionnaire		x	x	х
SIS full-form (emotional and handicap		х	х	х
domains only) questionnaire				
EQ-5D-5L questionnaire		х	x	х
ICECAP-A questionnaire		х	x	х
Health Literacy Questionnaire (HLQ)				х
Southampton Stroke Self-				х
Management Questionnaire (SSSMQ)				
SAE monitoring	х			
Review of general practice data				х
(number and nature of primary care				
visits, secondary care inpatient and				
outpatient visits, investigations,				
medications and use of social				
services, etc)				

**Table 1**: Frequency and timing of main variables and questionnaires.

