6.4. Randomisation

Once all invitation letters and reminders have been sent out to patients in a practice, the GP practice will be randomised to intervention or control (ratio of 1:1). Randomisation will be performed using a stratified, random permuted block design. The stratification factor will be GP practice size, split into two levels: $\leq 10,500$ and >10,500 patients.

Randomisation will be performed centrally by the study team who will then inform each practice about their allocation.

7. Interventions

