10.3. Economic evaluation

The long-term cost-effectiveness (cost-utility) of the new system of care (intervention package) compared with usual care will be determined in a within-trial economic evaluation.

Data will be collected on resource use implications of the intervention (including training), primary care visits, secondary care inpatient and outpatient visits, investigations, medications and use of social services, via electronic primary care records and patient questionnaires. Data on patient and carer-incurred costs will also be collected to allow analysis from a broader societal perspective. Data collection will be undertaken within the trial to determine the time taken to deliver the structured review, and any additional resources required. Attendance at the individual and group MLAS sessions will also be recorded for every participant, and each session will be costed, taking into account staff time, any consumables and use of the venue. Standard unit costs will be applied to health care resource use including NHS reference costs, the BNF for medications and Unit Costs for Health and Social Care (PSSRU).

The main outcomes of interest from the trial are quality of life (measured using EQ 5D-5L¹⁴ at baseline and six and twelve months after attendance at review) and capability (using the ICECAP-A questionnaire¹⁵). Both measures will be scored using the appropriate values sets.

Initially, a cost-consequence analysis will be performed, to present a disaggregated analysis of all mean resource use and costs related to the intervention and usual care, health care, social care, patient/carer costs and EQ-5D-5L and ICECAP-A scores at all time points. Quality-adjusted life years (QALYs) will be calculated by the area-under-the-curve method using responses at all time points, and adjusted for baseline covariates including EQ-5D-5L score. Multiple imputation will be undertaken where there is missing cost and outcome data. An incremental cost-utility analysis will then be undertaken to determine the cost per QALY gained of the intervention compared with usual care. Base-case analyses will be conducted from an NHS/Personal Social Services perspective, with a sensitivity analysis from a societal perspective, taking into account broader costs and outcomes.

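### Baseline EQ-5D-5L is collected after practice randomisation in an open-label trial, yet it is both a QALY covariate and the first point of the QALY curve, so the cost-utility result can be biased

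*SAP*

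**What the plan says.** The plan has two baseline questionnaires. For the first, SAP 6.5 states: "The primary outcome data will be collected via postal questionnaire at the time of invite to the study prior to Practice randomisation". The second carries SIS-SF, EQ-5D-5L and ICECAP-A, and these data "will also be collected by postal questionnaire after randomisation". Protocol 9.1 agrees on both. SAP 6.5 adds: "Non-responders to the secondary outcome questionnaire will be followed-up by telephone". SAP Table 1, SAP 9.3 and Protocol 8.2 all class the second set as baseline data.

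On the sequence of events, Protocol 6.4 says: "Once all invitation letters and reminders have been sent out to patients in a practice, the GP practice will be randomised". It continues: "Randomisation will be performed centrally by the study team who will then inform each practice about their allocation". SAP 6.3 accepts that "there is the potential for bias related to knowledge of the treatment arm assigned to each cluster (general practice) by patients, carers, clinicians". That section also counts the trial's own staff among those who may know the arm, and notes that some endpoints are subjective.

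Protocol 10.3 builds QALYs as an area under the curve over all time points, "adjusted for baseline covariates including EQ-5D-5L score". Baseline EQ-5D-5L therefore enters the QALY analysis twice. No document says when the second questionnaire is sent relative to the practice learning its arm, the patient learning it, or the first intervention contact.

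**The concern.** A baseline covariate is safe to adjust for because allocation cannot have affected it. That protection is lost for a self-reported score taken after allocation in an open-label trial. By then the practice knows its arm. An intervention practice may already have posted the needs checklist that goes out before the structured review (Protocol 7.1.1). No blinding is stated for the telephone calls to non-responders. If any of this moves the answers in one arm, adjustment treats the movement as a pre-existing difference and corrects the QALY comparison for it, wrongly. The same value also contributes directly to the QALY as the start of the curve.

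Cost-effectiveness is one of the two stated objectives (Protocol 5.2, SAP 5.1), and the incremental QALY is the denominator of the cost per QALY gained. A small error in it can matter if the true gain is also small.

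**Working it through.** The plan gives no figure to reproduce, so this is an illustration of size.

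**Inputs**
- From Protocol 10.3: EQ-5D-5L at baseline, 6 and 12 months; area under the curve; adjustment for baseline EQ-5D-5L.
- Assumed, because the documents give neither: a shift d of 0.01 to 0.03 index points in the intervention arm's baseline answers, and a within-arm slope b of each follow-up score on baseline of 0.5 to 0.7.
- Also assumed: no true effect, the same slope at 6 and 12 months, and baseline at time 0.

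**Step 1: QALY weights.** Two half-year trapezoids give 0.5 × (B + M6)/2 + 0.5 × (M6 + M12)/2 = 0.25B + 0.5M6 + 0.25M12.

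**Step 2: no adjustment.** The shift enters through B alone, so bias = 0.25d.
- 0.25 × 0.01 = 0.0025
- 0.25 × 0.03 = 0.0075

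**Step 3: adjusted for baseline EQ-5D-5L.** The slope of the QALY on B is 0.25 + (0.5 + 0.25)b = 0.25 + 0.75b. Bias = 0.25d − (0.25 + 0.75b)d = −0.75bd.
- −0.75 × 0.5 × 0.01 = −0.00375
- −0.75 × 0.7 × 0.03 = −0.01575

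In absolute value the range is about 0.004 to 0.016. The sign is opposite to the shift, whereas the unadjusted bias has the same sign as the shift.

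**Step 4: check by simulation** (400,000 patients, d = 0.03, correlation 0.65, equal variances, so that slope equals correlation). For the adjusted analysis the formula gives −0.75 × 0.65 × 0.03 = −0.0146 and the simulation −0.0146. For the unadjusted analysis both give 0.0075.

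**Step 5: wider assumptions.** With d from 0.02 to 0.05 and b from 0.5 to 0.8, the adjusted bias in absolute value runs from 0.75 × 0.5 × 0.02 = 0.0075 to 0.75 × 0.8 × 0.05 = 0.030. The unadjusted bias runs from 0.005 to 0.0125.

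**Step 6: what removes it.** Replacing only the covariate with pre-randomisation scores leaves 0.25d, because the affected value is still on the curve. If both arms also share one baseline value c, the QALY becomes 0.25c + 0.5M6 + 0.25M12 and d no longer appears.

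**The case against.** Four objections carry weight.

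- **No shift is demonstrated.** A reader might infer that patients knew their arm, or had begun the intervention, when they answered. The documents do not say so. The review forms part of the regular annual review, the MLAS leaflet is handed out there (Protocol 7.1.1), and MLAS is open only after a review (SAP 10.2.1), so MLAS exposure by then is less likely. This stands: the bias is possible, not shown.
- **Only EQ-5D-5L is affected as written.** A reader might infer that all three instruments are used for baseline adjustment. SAP 8.3 lists no baseline questionnaire score among its covariates. SAP 10.2 plans summary statistics for these instruments and defers analysis to the HEAP, which is not among the documents. For SIS-SF and ICECAP-A the risk depends on later models, either in the HEAP or under the discretion that SAP 8.3 leaves for secondary endpoints.
- **Non-response need not decide who has a QALY.** Protocol 10.3 plans multiple imputation for missing costs and outcomes, and non-responders are telephoned. Arm-dependent loss that the observed data do not explain could still matter, but QALYs are not restricted to those who return this questionnaire.
- **Some reporting is already planned.** SAP 9.1 records questionnaire dates and tabulates baseline return rates (Table 2.5), and SAP 9.3 gives baseline scores by arm. However, SAP 9 specifies missing data by arm only at 6 and 12 months, and nothing relates the second questionnaire's date to randomisation.

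None of this alters the post-randomisation timing or the double use of EQ-5D-5L in Protocol 10.3.

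**Conclusion.** The point holds for the cost-utility analysis. A score taken after allocation in an open-label trial is both covariate and curve point for QALYs, and the plan neither prevents nor examines a shift in it. Under the assumed shift and slope, the adjusted QALY difference would be biased by about 0.004 to 0.016. These figures scale directly with assumptions that the documents cannot confirm; with no shift the bias is zero, and the direction cannot be determined in advance.

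A reader might extend the point to the co-primary results. The documents do not support that: the baseline in those models is the SIS emotion or handicap score, which the plan collects before randomisation. No power or sample-size figure changes.

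**What to change.** **Practices not yet randomised, if any.** Send the second baseline questionnaire and close its return window before randomisation. Nothing need be added to the invitation pack. The cost is a few weeks' delay per practice. The SAP's table files are dated April 2020 and SAP 9.1 charts reviews from May 2018, so few or no practices may remain to benefit.

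**Practices already randomised.** Pre-specify in the HEAP a QALY sensitivity analysis that does both of the following:
- adjusts for pre-randomisation covariates (SIS emotion and handicap, age, gender, time since stroke) in place of baseline EQ-5D-5L;
- uses one common baseline EQ-5D-5L value in both arms as the first curve point.

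Both parts are needed. The limitation is that chance imbalance in EQ-5D-5L is then only partly corrected, which is a reason to read this analysis beside the planned one.

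**Reporting.** Give the return rate and date of the second baseline questionnaire by arm, relative to the practice's randomisation date. If the HEAP adjusts SIS-SF or ICECAP-A for baseline, apply the same covariate sensitivity analysis there.

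This uses data the trial already plans to collect; the cost is HEAP wording and a little more analysis work.
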